16 ADMINISTRATIVE PROCEDURES

16.1 Regulatory and Ethical Compliance

This clinical trial will be conducted in accordance with the principles of the Declaration of Helsinki, and in compliance with ISO 14155:2011 Clinical investigation of medical devices for human subjects, Good Clinical Practice (GCP), and the Code of Federal Regulations (CFR). The study will also be conducted in accordance with the Sponsor's Standard Operating Procedures (SOPs), and the SOPs of Contract Research Organizations participating in the conduct of the clinical trial, and all other applicable regulations. The Investigator and all clinical trial staff will conduct the clinical trial in compliance with this protocol. The Investigator will ensure that all personnel involved in the conduct of the clinical trial are qualified to perform their assigned duties through relevant education, training, and experience.

16.2 Informed Consent Procedures

Voluntary informed consent will be obtained from every subject prior to the initiation of any screening or other clinical trial-related procedures. The Investigator must have a defined process for obtaining consent. Specifically, the Investigator, or designee, will explain the clinical trial to each potential subject and the subject must indicate voluntary consent by signing and dating the IRB/IEC approved informed consent form. The subject must be provided an opportunity to ask questions of the Investigator, and if required by local regulation, other qualified personnel. The Investigator must provide the subject with a copy of the consent form written in a language the subject understands. The consent document must meet all applicable local laws and will provide subjects with information regarding the purpose, procedures, requirements, and restrictions of the clinical trial, along with any known risks and potential benefits associated with the investigational product, the available compensation, and the established provisions for maintaining confidentiality of personal, protected health information. Subjects will be told about the voluntary nature of participation in the clinical trial and will be provided with contact information for the appropriate individuals should questions or concerns arise during the clinical trial. The subject also will be told that their records may be accessed by appropriate authorities and Sponsor-designated personnel. The Investigator must keep the original, signed copy of the consent and must provide a duplicate copy to each subject.

16.3 Responsibilities of the Investigator and IRB/IEC

Before clinical trial initiation, this protocol, the informed consent form (and assent form, if applicable), any other written information provided to subject, and any advertisements

planned for subject recruitment must be approved by an Institutional Review Board / Independent Ethics Committee (IRB/IEC). Documentation of IRBs/IECs for this clinical trial can be found in the Trial Master File. The Investigator must provide documentation of IRB/IEC approval to the Sponsor. The approval must be dated and must identify the applicable protocol, amendments (if any), informed consent form, assent form (if any), all applicable recruiting materials, written information for subjects, and subject compensation programs. The IRB/IEC must be provided with a copy of the Investigator's Brochure, any periodic safety updates, and all other information as required by local regulation and/or the IRB/IEC. At the end of the clinical trial or in the case of early termination, the Investigator will notify the IRB/IEC of the clinical trial's final status. Finally, the Investigator will report to the IRB/IEC on the progress of the clinical trial at intervals stipulated by the IRB/IEC.

16.4 Sponsor and Monitoring Responsibilities

The Sponsor will designate a monitor to conduct the appropriate site visits at the appropriate intervals. The clinical investigation will be monitored to ensure that the rights and wellbeing of the subjects are protected; the reported data are accurate, complete, and verifiable from the source documents; the equipment used to assess variables in the clinical investigation is maintained and calibrated per manufacturer instructions and Sponsor requirements; and the study is conducted in compliance with the current approved protocol (and amendment[s], if applicable), with current GCP, and with applicable regulatory requirements.

All investigative sites will have a site initiation. Monitoring will be conducted periodically while the clinical study is ongoing. Monitoring methods may include site visits, telephone, written, and fax correspondence. The assigned CSM will contact each site at appropriate intervals. The Lead Clinical Site Manager (LCSM) will determine the frequency of site visits. Close-out visits will take place after the last visit of the last subject.

Enrollment will be tracked and reported at regular intervals. Details regarding enrollment (eg, number of subjects pre-screened, screened, reasons for screen failures, etc.) may be requested of the investigative site and must be provided within a reasonable time period.

The Sponsor will be responsible for implementing and maintaining quality assurance and quality control systems to ensure the study is conducted and data are generated, documented and reported in compliance with the protocol, GCP and applicable regulatory requirements. The Sponsor will secure agreement from all involved parties to ensure direct access to all study related sites, source data and documents, and reports for the purpose of monitoring and auditing by the Sponsor, and inspection by domestic and foreign regulatory authorities.

Quality control will be applied to each stage of data handling to ensure that all data are reliable and have been processed correctly. Agreements made by the Sponsor with the Investigator/Institution and any other parties involved in the clinical study will be provided in writing as part of the protocol or as a separate agreement.

16.5 **Regulatory Documentation and Records Retention**

Statistical Analysis Plan

PROTOCOL TMI-13-01 (ALCON PROTOCOL GLD122c-C001)

NCT03273907

Protocol Title:

Post Approval Study of the CyPass System in Patients with
Primary Open Angle Glaucoma Undergoing Cataract Surgery

[REDACTED]

[REDACTED]

Protocol TDOC Number:

TDOC-0052735

[REDACTED]

[REDACTED]

[REDACTED]

[REDACTED]

[REDACTED]

Approvals:

See last page for electronic approvals.

Job Notes:

This is the original (Version 1.0) Statistical Analysis Plan for this study. This version of the Statistical Analysis Plan is based on Version 4.0 of the study protocol.

Executive Summary:**Key Objectives:**

The primary objective of this study is to demonstrate that the rate of clinically relevant complications associated with CyPass Micro-Stent placement and stability using the CyPass 241-S applicer, as determined at 36 months in the post-market setting, is less than the pre-specified performance target, which is based on experience with the CyPass Model E applicer in the COMPASS (TMI-09-01) Trial.

Decision Criteria for Study Success:

This study is considered a success if the observed rate of clinically relevant complications associated with CyPass Micro-Stent placement and stability, as determined at 36 months, is less than the pre-specified performance target.

Table of Contents

Table of Contents	3
List of Tables.....	4
1 Study Objectives and Design.....	6
1.1 Study Objectives.....	6
1.2 Study Description	6
1.3 Masking	7
1.4 Interim Analysis.....	7
2 Analysis Sets.....	7
2.1 Intention to Treat Analysis Set	7
3 General Reporting Conventions	7
4 Study Conduct, Subject Baseline, and Surgical Summaries.....	8
4.1 Subject Disposition.....	8
4.2 Protocol Deviations	9
4.3 Demographic and Baseline Characteristics	9
4.4 General Medical and Ophthalmic History.....	9
4.5 Implantation Surgery	9
5 Effectiveness Analysis Strategy.....	9
5.1 Effectiveness Endpoints	9
5.1.1 Primary Effectiveness Endpoint	9
5.1.2 Secondary Effectiveness Endpoints.....	9
5.1.2.1 Effectiveness Hypotheses	10
5.1.3 Prior and Concomitant Ocular Medication Usage.....	11
6 Safety Analysis Strategy	11
6.1 Safety Endpoints.....	11
6.2 Primary Safety Endpoint	11
6.2.1 Safety Hypothesis	12
6.2.2 Analysis Methods	12
6.3 Secondary Safety Endpoints.....	12
6.3.1 Secondary Safety Hypotheses	13
6.3.2 Analysis Methods	13
6.4 Other Safety Outcomes.....	13
6.5 Additional Safety Assessments.....	14

6.5.1	Adverse Events	14
6.5.2	Device Deficiencies.....	16
6.5.3	Endothelial Cell Count	16
6.5.4	Gonioscopy and Slit Lamp Findings	16
6.5.5	Fundus Examination.....	16
6.5.6	Corneal Pachymetry	16
6.5.7	Intraocular Pressure	16
6.5.8	Visual Field Loss Mean Deviation Testing.....	17
6.5.9	Manifest Refraction	17
6.5.10	Best Corrected Visual Acuity (BCDVA)	17
6.5.11	CyPass Explantation and/or Repositioning	17
7	Sample Size and Power Calculations	17
8	References.....	18
9	Revision History	18
10	Appendix A: Schedule of Visits.....	19
11	Appendix B: Study Design	20
12	Appendix C: Data Sources.....	21
13	Appendix D: Cylinder Adjustment Converting Negative to Positive Notation....	28
14	Appendix E: Conversion of Visual Acuity Score to Snellen Values.....	28

List of Tables

Table 1-1	List of Abbreviations.....	5
Table 10-1	Schedule of Visits.....	19

Table 1-1

List of Abbreviations

ADE	Adverse device effect
AE	Adverse event
BCDVA	Best corrected distance visual acuity
CER	Clinical evaluation report
CI	Confidence interval
CRF	Case report form
CSR	Clinical study report
ICF	Informed consent form
IOP	Intraocular pressure (mmHg)
ITT	Intention to treat
logMAR	Logarithm of the Minimum Angle of Resolution
MedDRA®	Medical Dictionary for Regulatory Activities
MRSE	Manifest refraction spherical equivalent
OAG	Open angle glaucoma
OD	Right eye
OS	Left eye
OU	Both eyes
PAS	Post approval study
POAG	Primary open angle glaucoma
PT	Preferred term
SADE	Serious adverse device effect
SAE	Serious adverse event
SAP	Statistical analysis plan
SD	Standard deviation
SOC	System organ class
SSI	Secondary surgical intervention
TEAE	Treatment emergent adverse event
WHO	World Health Organization

1 Study Objectives and Design

This statistical analysis plan (SAP) describes the statistical analysis outlined in Section 15 of the study protocol (Version 4.0) along with any additional analyses planned before database lock (DBL).

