15.5.1.1 Statistical Hypothesis

The primary null hypothesis to be tested is that the observed rate of clinically relevant complications associated with CyPass Micro-Stent placement and stability is greater than or equal to the performance target rate of 7%. The corresponding alternative hypothesis to be tested is that the observed rate of complications is less than the performance target rate. These hypotheses are expressed formulaically as:

$$H_0: p_C \geq 7\%$$

$$H_1: p_C < 7\%$$

where p_C is the population proportion of eyes experiencing a complication event at 36 months.

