6.2.1 Safety Hypothesis

The primary null hypothesis to be tested is that the observed rate of clinically relevant complications associated with CyPass Micro-Stent placement and stability is greater than or equal to the performance target rate of 7%. The corresponding alternative hypothesis to be tested is that the observed rate of complications is less than the performance target rate. These hypotheses are expressed formulaically as:

$$\begin{aligned} H_0: p_c &\geq 7\% \\ H_1: p_c &< 7\% \end{aligned}$$

where p_c is the population proportion of eyes experiencing a complication event at 36 months.

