6.2.2 Analysis Methods

The primary safety hypothesis will be tested with an exact one-sided binomial test with type I error 0.05. This endpoint will be summarized by numerator (number of eyes meeting the endpoint), denominator (number of eyes in the ITT set), and the rate of ITT eyes meeting the endpoint. In addition, a summary of each individual complication type included in the primary safety endpoint (and a listing of these complications) will be provided.

Otherwise, no formal statistical hypothesis testing is planned for this study.

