6.5.11 CyPass Explantation and/or Repositioning

A listing detailing subjects with CyPass explantation and/or repositioning will be provided. The listing will include the following variables: site-subject, age, sex, race, ethnicity, explantation or repositioning event, surgery date, study day, and reason. The data for this listing will be collected on the adverse events eCRF. Further details can be found in Appendix C: Data Sources.

7 Sample Size and Power Calculations

The performance target for the primary safety endpoint is 7.0%.

An evaluation of COMPASS (TMI-09-01) data showed that through 24 months of follow-up, there were two eyes with failures to implant and eight eyes with CyPass malposition events, respectively, corresponding to the above definitions. In addition, there were four eyes with documentation of three rings visible within the first postoperative week that likely would have undergone early secondary surgical intervention due to anterior CyPass positioning under the approach documented in the Instructions for Use (IFU). Inclusion of these cases would increase the number of observed events from 10 to 14 (3.74%, 95% confidence

interval: 2.1% – 6.2%). Of note, not all investigators documented the number of rings visible in the early postoperative period because this was not a study requirement (data regarding the number of rings is recorded for only 96 subjects at 1 Day and 139 subjects at 1 Week), so this number likely underestimates the number of subjects who would have been candidates for early surgical re-intervention under the new criteria described in the IFU.

Based on these considerations, the “true” event rate is assumed to be 4.0%, and the performance target is set to 7.0%. The following assumptions were used for the sample size calculation:

- ≠ Type I error = 0.05
- ≠ one-sided alternative

With a sample size of 360 subjects in the final analysis (unilateral implants only) and a performance target of 7.0%, assuming a true event rate of 4.0%, there is 80% power to reject the null hypothesis based on a one-sided alpha = 0.05-level exact test for a single proportion.

To allow for attrition over this 36-month study, a cumulative rate of up to 20% of subjects lost to follow-up is assumed, corresponding to a targeted implantation of 450 eyes in 450 subjects to achieve at least 360 eyes with 36 months of follow-up.

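### The SAP declares success whenever the observed complication rate is below 7%, which contradicts its own exact 0.05-level test and gives about a 51% false-positive rate at 450 eyes

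*SAP*

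**What the plan says.** Under its heading on decision criteria, the SAP Executive Summary states: "This study is considered a success if the observed rate of clinically relevant complications associated with CyPass Micro-Stent placement and stability" falls below the target at the 36-month assessment. It mentions no test, p-value or confidence limit.

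SAP 6.2.2 gives a different rule: "The primary safety hypothesis will be tested with an exact one-sided binomial test with type I error 0.05". Protocol 15.5.1.2 and the Primary Analysis entry of the Protocol synopsis specify the same test. SAP section 7 sets the target ("The performance target for the primary safety endpoint is 7.0"%) and the planning rate ("event rate is assumed to be 4.0"%), and rests the sample size on the test: "there is 80% power to reject the null hypothesis based on a one-sided alpha = 0.05-level exact test for a single proportion".

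The sentences introducing the hypotheses are also phrased in terms of the estimate. SAP 6.2.1 begins: "The primary null hypothesis to be tested is that the observed rate of clinically relevant complications". Protocol 15.5.1.1 says: "The corresponding alternative hypothesis to be tested is that the observed rate of complications is less than the performance target rate". The formulas beneath both sentences use p_C, which is defined as the population proportion.

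**The concern.** A point estimate below 7% is much weaker evidence than rejection of H0: p ≥ 7% at the 5% level. Over a range of event counts the same data would be a success by the Executive Summary and a failure by SAP 6.2.2.

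This is the only formal hypothesis test in the study, and it is on the primary safety endpoint. If the Executive Summary rule is applied, the 5% type I error is lost, and the 80% power figure no longer describes the chance of declaring success. The study is open-label (SAP 1.3) and counts of primary-endpoint events are reported at every interim (SAP 1.4). A choice between the two rules made later would therefore be made with the accumulating results known.

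**Working it through.** **Inputs**
- Target p0 = 7.0%, planning rate p1 = 4.0%, one-sided exact test at 0.05, 360 eyes in the final analysis: SAP section 7 and Protocol 15.8.
- Planned implants: 360 / (1 − 0.20) = 450, same sections.
- Denominator of the primary rate: all ITT eyes, meaning those with an attempted implant (SAP 2.1, 6.2 and 6.2.2). The planned value is about 450.

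Let X be the number of eyes with an event, X ~ Binomial(n, p).

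**Step 1. Reproduce the plan's power.** The exact test rejects when X ≤ c, where c is the largest count with P(X ≤ c | n, 7%) ≤ 0.05. For n = 360:
- P(X ≤ 17 | 7%) = 0.0499 and P(X ≤ 18 | 7%) = 0.0783, so c = 17 (4.72%).
- Power at 4%: P(X ≤ 17 | 4%) = 0.8016.

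The stated 80% reproduces, so the sample size rests on the exact test.

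**Step 2. The exact test at the planned ITT size.** For n = 450:
- P(X ≤ 22 | 7%) = 0.0429 and P(X ≤ 23 | 7%) = 0.0649, so c = 22 (4.89%).
- Power at 4%: 0.860.

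**Step 3. The Executive Summary rule.** It is met when X/n < 0.07.
- n = 450: 0.07 × 450 = 31.5, so X ≤ 31 (31/450 = 6.89%).
- n = 360: 0.07 × 360 = 25.2, so X ≤ 25 (25/360 = 6.94%).

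**Step 4. Probability of declaring success**

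| n | Rule | Events allowed | True 4% | True 7% | True 8% |
|---|---|---|---|---|---|
| 450 | Observed rate < 7% | ≤ 31 | 99.9% | 51.1% | 22.0% |
| 450 | Exact test | ≤ 22 | 86.0% | 4.3% | 0.7% |
| 360 | Observed rate < 7% | ≤ 25 | 99.7% | 53.6% | 26.6% |
| 360 | Exact test | ≤ 17 | 80.2% | 5.0% | 1.0% |

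For n from 340 to 460, the Executive Summary rule's error rate at a true 7% lies between 47% and 55%. It varies because the event count is discrete.

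**Step 5. Where the rules disagree.** They conflict at 23 to 31 events of 450, or 18 to 25 of 360. For n = 450 the chance of landing there is P(X ≤ 31) − P(X ≤ 22):
- true 4%: 0.9986 − 0.8597 = 14%
- true 5%: 0.9693 − 0.5130 = 46%
- true 6%: 0.8159 − 0.1873 = 63%
- true 7%: 0.5106 − 0.0429 = 47%

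Rates of 5% and 6% lie inside the plan's own 95% interval for the COMPASS rate (2.1% to 6.2%).

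**Step 6. A case at the edge.** With 31/450, the Executive Summary rule gives success, the exact p-value is 0.51, and the one-sided 95% Clopper–Pearson upper limit is 9.18%. For comparison, 22/450 gives an upper limit of 6.91% and 23/450 gives 7.16%.

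**The case against.** The best reply is that this is loose drafting in a summary. Every methods passage specifies the exact test, SAP section 3 again describes the primary endpoint as a one-sided test at 0.05, and SAP section 1 says the SAP describes the analysis outlined in Protocol section 15. The hypothesis sentences also say observed rate but go straight on to p_C, the population proportion. Read in the same way, the success criterion merely restates H1.

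That is probably the intent, but the documents do not settle it. SAP section 1 is not a precedence clause, and the Protocol section it points to repeats the observed-rate wording. Nowhere is success defined as rejecting H0, so the one explicit decision rule is the point-estimate rule.

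Three narrower points stand and limit the claim:
- The error rate applies only if the Executive Summary rule governs, and it is evaluated at the null boundary. About 51% belongs to n = 450; it is 54% at n = 360.
- At the planning rate of 4% the rules disagree about 14% of the time, not 47%.
- The 80% power figure remains correct for the exact test. Under the Executive Summary rule the chance of success at 4% would be higher (99.7% at n = 360), so power does not fall short. What is lost is control of false success.

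**Conclusion.** The concern holds. The SAP's stated success criterion and its primary test are different rules, and the plan does not rank them. Taken as written, the criterion declares success with probability 51% (n = 450) or 54% (n = 360) when the true rate is exactly 7%, against 4.3% and 5.0% for the exact test.

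The figures assume independent eyes with a common event probability, and every eye in the denominator classified as event or no event. The 450-eye figures also assume that the planned ITT size is reached. The test itself, its alpha and the power calculation are sound; the faults are in the success criterion and in the hypothesis wording that echoes it. This must be corrected before the analysis, because it determines what the study may claim on its primary safety endpoint.

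**What to change.** In the SAP Executive Summary, replace the criterion with: *The study is a success if the exact one-sided binomial test rejects H0: p_C ≥ 7% at alpha 0.05, equivalently if the exact (Clopper–Pearson) one-sided 95% upper confidence limit for the 36-month rate is below 7%.*

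Name the exact limit, because other intervals can disagree with the test. At 23/450 a Wald upper limit is 0.0511 + 1.645 × √(0.0511 × 0.9489 / 450) = 6.82%, while the exact p-value is 0.065.

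Give the event limits for illustration: at most 22 of 450, or 17 of 360. State that the binding limit is recalculated for the actual ITT count, since SAP 6.2.2 fixes the ITT set as the denominator.

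In SAP 6.2.1, Protocol 15.5.1.1 and the Primary Analysis entry of the Protocol synopsis, replace the reference to the observed rate with the true (population) rate.

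The cost is wording only. No additional patients, visits or data are needed, and the sample size does not change.

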1.1 Study Objectives

To demonstrate that the rate of clinically relevant complications associated with CyPass Micro-Stent placement and stability using the CyPass System (Model 241-S) as determined at 36 months in the post-market setting is less than the pre-specified performance target, which is based on experience with the CyPass Model E applier in the COMPASS (TMI-09-01) trial.

1.2 Study Description

This study is a prospective, non-randomized, multicenter, single arm, post approval study of the CyPass System. Following routine cataract surgery, one CyPass Micro-Stent will be implanted into one study eye of each qualified subject. If both eyes qualify for the study, the eye with the worse BCDVA will be the study eye. If BCDVA in both eyes is the same, then the study investigator will choose which eye will be the study eye. Unless specified otherwise, ocular results refer to the study eye only. Therefore, throughout this SAP and corresponding tables and data listings the number of subjects and eyes are synonymous.

Subject participation in this study is expected to last up to 37.5 months and include 10 study visits. Within 42 days of screening, qualified subjects will receive cataract surgery followed by implantation of the CyPass Micro-Stent in one eye (the study eye) at the surgery visit. Eight postoperative follow-up visits are planned to occur at 1 day, 1 week, 1 month, 3 months, 6 months, 12 months, 24 months, and 36 months after surgery. Further details are provided in Appendix A: Schedule of Visits and Appendix B: Study Design. Upon completion of the 36-month follow-up visit, subjects will be exited from the study.

This post-approval study is designed to provide continued reasonable assurance of the safety and effectiveness of the device.

